# 3.5.4.1.2 Efficacy Endpoints

An initial description of efficacy measurements is provided in Section 3.3.1.

The primary efficacy endpoint of interest will be fungal-free survival at two weeks posttherapy. Fungal-free survival is defined as those patients who survived at the time point of interest and had documented microbiological eradication of *Candida* sp. from follow-up cultures collected after the initiation of study therapy. Microbiological eradication denotes negative follow-up cultures for *Candida* sp. from the site of infection at the time of evaluation. If a culture is not obtained on the day of assessment, the last culture after study entry may be used to assist in the assessment of microbiological eradication. If the last culture is negative for *Candida* sp., then microbiological eradication would be considered achieved. Fungal-free survival also assumes no additional antifungal therapy is required for the treatment of the underlying *Candida* infection once study therapy has ended; however, once study therapy has ended, prophylaxis with an antifungal agent (e.g., fluconazole) may be administered, if this is deemed appropriate by the investigator.

The secondary efficacy endpoint will be fungal-free survival at the end of study therapy.

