# 3.5.5 Analysis Populations

# 3.5.5.1 Efficacy Analysis Populations

All efficacy evaluations will use the Full Analysis Set (FAS) patient population, which includes those patients who receive at least 1 full dose of study therapy and have a documented (culture-confirmed) diagnosis of invasive candidiasis. All patients, irrespective of body weight at study entry, will be grouped together for the primary evaluation. Subgroup evaluation based on the 3 body weight categories at study entry (<1000 grams, 1000-1500 grams, >1500 grams) will also be displayed.

A supportive analysis using the Per-Protocol population will be performed for the primary and secondary efficacy endpoints. The Per-Protocol population excludes patients due to important deviations from the protocol that may substantially affect the results of the primary and secondary efficacy endpoints. Inclusion within the per-protocol population mandates meeting all of the following:

- The patient must have a documented (culture-confirmed) diagnosis of invasive candidiasis.
- The patient must not receive >1 day of concomitant systemic antifungal therapy while on study therapy, if the total duration of study therapy is 3 weeks or less. For durations of study therapy exceeding 3 weeks, the patient must not receive concomitant systemic antifungal therapy while on study therapy, that amounts to more than 5% of the total duration of study therapy.
- The patient must have a 2-week posttherapy efficacy evaluation, including an appropriate microbiological assessment completed either at this visit or confirmed prior to that visit.
- The patient must receive at least 5 full days of study therapy.

The patient must not commit any protocol violations that interfere with the assessment of efficacy.

The final determination on protocol violations, and thereby the composition of the Per-Protocol population, will be made prior to the final unblinding of the database and will be documented in a separate memo. A patient who violates the protocol at randomization (e.g., certain inclusion or exclusion criteria, such as the use of prohibited prior treatment) will be excluded from the Per Protocol population. For patients who violate the protocol during the study (e.g., taking prohibited concomitant medication), data obtained subsequent to the violation will be excluded from analysis.

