## 3.5.8 Sample Size and Power Calculations

# 3.5.8.1 Sample Size and Power for Efficacy

This study will randomize approximately 90 patients at a 2:1 ratio into either the caspofungin treatment group (N = 60) or the amphotericin B deoxycholate treatment group (N = 30) and has 80% power to demonstrate the superiority of caspofungin over amphotericin B deoxycholate at an overall two-sided, 5% alpha-level, if the underlying treatment difference in fungal-free survival at 2 weeks posttherapy is approximately 30 percentage points (or larger). Randomization of approximately 90 patients should

b Includes only those endpoints not pre-specified as Tier 1 or not already pre-specified as Tier-2 endpoints.

**Protocol/Amendment No.:** 064-02

yield approximately 84 FAS evaluable patients, assuming an approximate 5% drop-out rate. The power and sample size are based on an underlying response rate of 50% for the amphotericin B deoxycholate treatment group, based on a review of the available data in the literature, including the recent comparative efficacy and safety study of caspofungin versus amphotericin B deoxycholate in which a favorable response was observed in 41.7% of amphotericin B deoxycholate-treated patients (see Table 3-1) [9]. On balance, the literature suggests most currently available antifungal agents are associated with successful outcomes in 40-80% of the patients [9, 24, 26, 30-36]; however, the efficacy with amphotericin B deoxycholate from the recent analysis was on the lower end (~40%) [9]. The caspofungin data from retrospective analyses and the recent comparative study demonstrated a relatively high success rate (80-100%) [9-13]. The minimum criterion for success is that the lower bound of 95% CI for the difference between the 2 treatment groups (caspofungin minus amphotericin B deoxycholate) in the primary efficacy endpoint is >0. Given the assumed response rate in the amphotericin B deoxycholate treatment group, this may occur when the observed difference between treatment groups is approximately 30 percentage points (or larger).

Assuming the same 2:1 randomization ratio and superiority hypothesis with 80% power, Table 3-8 displays sample size requirements for a few favorable response rate combinations, along with the difference and 95% CI for the difference.

Table 3-8

Superiority Sample Size Projections

Based on 80% Power and 2:1 (Caspofungin:Amphotericin B Deoxycholate)

Allocation Ratio

1 modulon runo					

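### The Per-Protocol criteria make no exception for death, so they drop infants who die before 5 full days of therapy and, read literally, all who die before the 2-week visit, although death fails the endpoint

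*Combined protocol and SAP*

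**What the plan says.** - **Endpoint (Section 3.5.4.1.2).** "Fungal-free survival is defined as those patients who survived at the time point of interest", with documented eradication as the second component. Death by the time point is therefore a failure. The secondary endpoint is the same measure at the end of therapy.
- **PP membership (Section 3.5.5.1).** All listed criteria must be met. Two matter here: "The patient must have a 2-week posttherapy efficacy evaluation, including an appropriate microbiological assessment" and "The patient must receive at least 5 full days of study therapy". The rest of the first criterion lets the microbiological part be settled before the visit. It says nothing about infants who have died.
- **Timing of the evaluation (Section 3.2.3.5.2).** The fungal-free survival evaluation is made at the 2-week posttherapy visit.
- **Missing data (Tables 2-2 and 3-6).** The FAS analysis counts missing data as failure. The PP analysis uses observed data.
- **Role of the PP set (Sections 3.5.5.1 and 3.5.6.1).** It supports both the primary and the secondary efficacy endpoints. The only other sensitivity analysis is conditional on 3 or more patients receiving the wrong drug throughout treatment.

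**The concern.** Section 3.5.5.1 describes the PP set as leaving out patients with important protocol deviations. Dying is not a deviation; it is one of the two ways to fail the endpoint. When death also bars entry to the analysis set, membership depends on the outcome, and the arms are compared among infants selected on survival.

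The distortion can run either way. If deaths are commoner on amphotericin B, the PP estimate understates the benefit of caspofungin. If they are commoner on caspofungin, it masks harm. Because the same PP set serves the end-of-therapy endpoint, deaths on therapy can be lost there too. A reader who looks to the PP result to confirm the FAS result could be misled about how robust it is.

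**Working it through.** **Inputs from Section 3.5.8.1.** "This study will randomize approximately 90 patients at a 2:1 ratio" (60 caspofungin, 30 amphotericin B). The trial "has 80% power to demonstrate the" superiority of caspofungin "at an overall two-sided, 5% alpha-level". On the control rate: "The power and sample size are based on an underlying response rate of 50" percent. The assumed "treatment difference in fungal-free survival at 2 weeks posttherapy is approximately 30" percentage points, so the planning rates are 80% versus 50%.

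**Reproducing the plan's figure.** Table 3-8 gives 84 (56:28) for 80% versus 50%. Use the pooled-variance formula without continuity correction, with k = 2 and a pooled rate of (0.50 + 2 × 0.80)/3 = 0.70:

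n(control) = [1.960 × √(1.5 × 0.70 × 0.30) + 0.842 × √(0.50 × 0.50 + 0.80 × 0.20/2)]² / 0.30² = (1.100 + 0.483)² / 0.09 ≈ 27.9, rounded up to 28.

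This gives 28 + 56 = 84, an exact match.

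**Checking the interval method.** Miettinen-Nurminen intervals were computed for two tabulated cases.
- 45/56 versus 14/28 gives 30.4 (9.2 to 50.4). Table 3-8 has 30 (9.3 to 50.3).
- 3/60 versus 3/30 gives -5.0 (-21.3 to 5.9). Table 3-9 has -5.0 (-21.2 to 5.9).

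**Starting point.** 60 × 0.80 = 48 and 30 × 0.50 = 15. So 48/60 versus 15/30 is +30.0 points (95% CI 9.5 to 49.5). The PP set gives the same result if deaths stay in as failures and nobody else is excluded.

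**Removing deaths.** Every death is already a failure, so removal shrinks the denominators and leaves the numerators alone:

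PP difference = 48/(60 - deaths on caspofungin) - 15/(30 - deaths on amphotericin B)

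The documents give no death rates by arm for this trial, so the counts below are assumptions.

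| Deaths removed (caspofungin / amphotericin B) | PP counts | PP rates | Difference |
|---|---|---|---|
| 0 / 0 | 48/60 vs 15/30 | 80.0% vs 50.0% | +30.0 |
| 1 / 2 | 48/59 vs 15/28 | 81.4% vs 53.6% | +27.8 |
| 3 / 3 | 48/57 vs 15/27 | 84.2% vs 55.6% | +28.7 |
| 3 / 6 | 48/57 vs 15/24 | 84.2% vs 62.5% | +21.7 |
| 6 / 9 | 48/54 vs 15/21 | 88.9% vs 71.4% | +17.5 |
| 6 / 12 | 48/54 vs 15/18 | 88.9% vs 83.3% | +5.6 |

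The 95% intervals for the last three rows are 1.6 to 43.5, -1.0 to 40.3 and -10.4 to 29.4. The 1/2 row is the kind of loss to expect if only deaths before 5 full days are removed. The 6/12 row (10% versus 40% mortality) requires the literal reading, in which every death before the 2-week visit is removed.

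**The opposite direction.** Assume 80% eradication among survivors in both arms, with mortality of 20% on caspofungin and 10% on amphotericin B. The FAS rates are 0.80 × 0.80 = 64% and 0.90 × 0.80 = 72%, a difference of -8 points. With all deaths removed, the PP rates are 80% and 80%, a difference of 0.

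**Are deaths likely to be few?** The documents do not suggest so. Section 1.4 cites mortality of about 30% for *Candida* urinary infection, and Table 3-3 lists one trial with 6/11 survival on amphotericin B. Neither is a forecast for this trial.

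**The case against.** The strongest objection is that the text does not settle the status of a later death. Sections 2.5 and 3.3.1 base the assessment on all available data. A recorded death determines the endpoint, and it is an observed outcome, so the observed-data rule does not by itself remove it. Table 3-6 also names survival through the 2-week period as the PP endpoint, and its survival component would be empty if every PP infant had to be alive. This stands: the sponsor may intend a documented death to count as the 2-week evaluation. A reader might infer that the PP analysis can show no mortality difference at all. That follows only from the literal reading.

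A reader might also infer that the trial's conclusion is biased, or that the FAS and PP results can never be compared. The documents do not support either. The success criterion belongs to the primary analysis in the FAS, where death fails by definition and missing data count as failure. Death is a serious adverse experience (Table 3-5), and the serious-event comparison carries a between-group 95% CI in all treated patients (Table 3-7, Section 3.5.5.2). PP membership is fixed and documented before final unblinding, so a gap between the two results can be traced to the excluded infants. Fixing membership blind does not, however, undo selection on outcome.

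Finally, a minimum-exposure rule is a common PP convention, and exclusion criterion 9 bars infants not expected to survive 5 days. That limits early deaths but does not rule them out, because it rests on expectation.

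**Conclusion.** The point holds for the supportive analyses. Loss of infants who die before 5 full days is certain as written. Loss of later deaths follows from the literal text but may not be intended. The consequence is a PP estimate that can understate or hide a mortality difference in either direction, for both efficacy endpoints.

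The shift could be about 2 points (30.0 to 27.8) if only a few early deaths are lost, or more than 24 points (30.0 to 5.6) if many later deaths are lost and they fall mainly on amphotericin B. All these figures rest on assumed death counts applied to the planning rates, with no other PP exclusions. The primary analysis, its power and the success criterion are untouched.

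It is tempting to extend the argument to every infant who fails before the visit. The documents do not support that. They define no established-failure category, and Section 3.5.4.1.2 lets the last culture decide eradication, so a positive culture before the visit does not fix the outcome.

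**What to change.** Add to Section 3.5.5.1, before unblinding:

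- An infant who otherwise meets the PP criteria and dies before the 2-week posttherapy visit remains in the PP set as a failure.
- A documented death satisfies the 2-week-evaluation criterion and is exempt from the 5-day minimum.
- For the end-of-therapy endpoint, deaths through the end of therapy count as failures.

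The cost is a few lines of text and no extra data, since Section 3.2.3.7.1 already asks for an efficacy assessment at discontinuation and continued follow-up. The downside is small: the PP set will include a few infants with little exposure. The result with the 5-day minimum applied to deaths can be shown alongside, so that the effect of the choice is visible.

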#### 3.2 STUDY PROCEDURES

# 3.2.1 Concomitant Medication(s)/Treatment(s)

Drugs specifically excluded in the exclusion criteria must not be administered. Medications not permitted at any time during course of study therapy include rifampin and any systemic antifungal agent (oral or IV) other than the study therapy.

Should there be a clinical indication for any additional medication during the course of the study, the name of the drug, dosage (if required), and date(s) of administration must be recorded on the appropriate electronic case report form (eCRF).

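### In the Per-Protocol analysis, discarding data after an on-study violation deletes the one 2-week outcome that Per-Protocol membership requires

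*Combined protocol and SAP*

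**What the plan says.** Section 3.5.5.1 defines the Per-Protocol (PP) set and then adds a handling rule. The rule begins "For patients who violate the protocol during the study (e.g., taking prohibited concomitant medication" and ends "data obtained subsequent to the violation will be excluded from analysis".

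The same section sets the membership criteria:
- With study therapy of 3 weeks or less, the disqualifying event is to "receive >1 day of concomitant systemic antifungal therapy while on study therapy, if the total duration of study therapy is 3 weeks or less".
- With longer therapy, the disqualifying event is concomitant systemic antifungal use which "amounts to more than 5% of the total duration of study therapy", a limit relative to course length.
- A third criterion concerns the outcome: "The patient must have a 2-week posttherapy efficacy evaluation, including an appropriate microbiological assessment completed either at this visit or confirmed prior to that visit".
- There are further criteria for a minimum of 5 full days of study therapy and for the absence of violations that interfere with the efficacy assessment.

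Section 3.2.1 defines what is prohibited: drugs that are not, in its words, "permitted at any time during course of study therapy include rifampin and any systemic antifungal agent (oral or IV) other than the study therapy".

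Section 3.5.4.1.2 places the primary endpoint, fungal-free survival, at 2 weeks posttherapy and the secondary endpoint at the end of study therapy. If no culture is taken on the assessment day, "the last culture after study entry may be used to assist in the assessment of microbiological eradication". Antifungal treatment of the index infection after study therapy has ended is incompatible with fungal-free survival.

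Section 3.5.6.1 and Table 3-6 count missing data as failure in the FAS, which is primary, and use observed data in PP, which is supportive.

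**The concern.** A rule that cuts the record at the violation suits repeated measurements, where the earlier visits still carry information. Here there is one binary reading per time point, and the primary one comes 2 weeks after therapy ends. Any violation during therapy precedes it, so cutting the record removes the outcome. The end-of-therapy endpoint is normally lost too.

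The example chosen, prohibited concomitant medication, includes systemic antifungals. Section 3.2.3.7.1 lists the need for another systemic antifungal among the reasons to stop study therapy, beside lack of improvement and progression. Loss of outcome after such use may therefore be informative. That section also keeps infants under efficacy follow-up after study therapy stops, so the rule can discard results the sites were told to collect.

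At stake is whether the supportive PP result is a reliable check on the FAS result, and whether two analysts would produce the same one.

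**Working it through.** **1. The rules side by side, by type of infant**

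| Infant | Rule that decides | Does the discard sentence matter? |
|---|---|---|
| Concomitant antifungal over 1 day (therapy ≤3 weeks) or over 5% of duration (longer therapy) | Membership: out of PP | No |
| Fewer than 5 full days of study therapy | Membership: out of PP | No |
| Antifungal for the index infection after study therapy has ended | Endpoint definition, 3.5.4.1.2: failure | No; 3.2.1 prohibits only during study therapy |
| Concomitant antifungal at or below the threshold, other criteria met | Membership: kept, 2-week evaluation required | Yes: that evaluation is then discarded |
| Another on-study violation judged not to interfere with efficacy assessment | Membership: kept | Yes, in the same way |

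The conflict is confined to the last two rows. For longer courses the permitted overlap is more than a day: 5% of 42 days is 2.1 days, and 5% of the 90-day maximum is 4.5 days.

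**2. What happens to an affected infant.** The text allows more than one answer. Under observed data, the infant is missing and drops out. Under the 2-week evaluation criterion, the infant leaves PP, with the same effect. No text makes the infant a PP failure.

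**3. The plan's sample size.** Inputs from Section 3.5.8.1: 80% vs 50%, 2:1, two-sided 5%, 80% power. With p̄ = (0.5 + 2×0.8)/3 = 0.7:

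n(control) = [1.960·√(1.5×0.7×0.3) + 0.842·√(0.5×0.5 + 0.8×0.2/2)]² / 0.3² = (1.100 + 0.483)² / 0.09 ≈ 27.9, so 28.

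The total is 84 (56:28), as in Table 3-8. The sample size is not in question.

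**4. Sensitivity per infant.** The documents give no rate of such violations and no projected PP size. I assume k = 1 to 4 affected failures in one arm and start from 45/56 vs 14/28. The Miettinen-Nurminen interval there is 30.4 points (9.2 to 50.4), within 0.1 point of the limits in Table 3-8. Dropping k failures gives 14/(28−k) for amphotericin B or 45/(56−k) for caspofungin.

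| k | Amphotericin B failures dropped: difference (lower bound) | Caspofungin failures dropped: difference (lower bound) |
|---|---|---|
| 1 | 28.5 (7.2) | 31.8 (10.7) |
| 2 | 26.5 (5.2) | 33.3 (12.3) |
| 3 | 24.4 (3.1) | 34.9 (14.0) |
| 4 | 22.0 (0.8) | 36.5 (15.8) |

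One amphotericin B failure moves the difference by about 2 points. If the dropped infant was a success, the shift reverses: 45/56 − 13/27 = 80.4% − 48.1% = 32.2 points.

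**The case against.** The strongest reply is that other rules decide most infants given additional antifungals. Above the thresholds they leave PP as patients. Once study therapy stops, further antifungal treatment is no longer prohibited medication and is already an endpoint failure. PP is only supportive, no non-inferiority claim rests on it, and its composition is fixed and documented before unblinding. All of this stands and limits the point to a small group.

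Three stronger readings are tempting, and the documents do not support them.

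- **Failures become successes.** A reader might infer that an affected infant is scored on an earlier negative culture. The last-culture provision applies when no culture was taken on the assessment day, not when a result was taken and set aside. Survival to 2 weeks would also have been discarded, and PP requires a 2-week evaluation. The text does not clearly rule this route out, since the microbiological part may pre-date the visit, but it does not state it. If it were used, 1 to 4 amphotericin B failures would give differences of 26.8, 23.2, 19.6 and 16.1, with the lower bound below zero from the third (−0.4). The same number of caspofungin failures would give 32.1 to 37.5.
- **All rescued failures are affected.** Applying a rescue fraction of 10% to 30% to every failure in both arms turns a true 30 points into 29.0 to 26.3. That fraction has no source in the documents. Infants above the thresholds would leave PP with or without the sentence.
- **The primary result is biased.** The sentence does not name PP, so a reader might carry it to the FAS. It sits in the PP paragraph, and in the FAS missing counts as failure. That protection would fail only if an earlier culture were substituted first.

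The reply does not remove the contradiction for infants whom the membership criteria keep.

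**Conclusion.** The point holds in a limited form. For infants who stay in PP after an on-study violation, Section 3.5.5.1 both requires the 2-week evaluation and discards it. This is a stated rule that defeats the criterion beside it, not merely a missing detail. The consequence is loss, possibly informative, of outcomes from a supportive analysis.

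The size cannot be determined from the documents. The 2-points-per-infant figure assumes that the planned evaluable numbers carry over to PP; a smaller PP set would make each infant weigh more. The direction depends on which arm has more affected infants and on their outcomes. The primary FAS conclusion is not affected on the natural reading. The sentence should be corrected before unblinding.

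**What to change.** In Section 3.5.5.1, state that the discard sentence does not apply to the binary fungal-free survival endpoints, at the end of therapy or at 2 weeks, in either analysis set. Then:

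- Handle on-study violations only through the stated PP membership criteria.
- For every infant kept in PP, use the observed outcome to the 2-week visit under the Section 3.5.4.1.2 definition. Antifungal treatment of the index infection after study therapy ends remains a failure, as that section already has it.
- Do not substitute a culture from before the violation for a later result that was obtained.

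This does not require counting a brief permitted overlap on therapy as a failure. It also leaves the thresholds unchanged, so infants above them stay outside PP.

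The cost is SAP wording only, with no new data. PP figures may move slightly in either direction.
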